## 9 Effectiveness Analysis

Unless otherwise stated, all effectiveness analyses will be conducted primarily using the ITT Population. The analyses may be reproduced using the Per-Protocol Population if the PP Population contains less than 90% of the subjects in the ITT Population.

### 9.1 Primary Effectiveness Endpoint

The primary endpoint is defined as the change from Baseline based on the Blinded Evaluator's live assessment at 3 months after last treatment using the GCRS. The change from Baseline to 3 months after last treatment GCRS Blinded Evaluator will be calculated using the equation specified in [Section 4.4](#).

Galderma

Protocol number: 43USCH2208

Protocol V4.0

**9.1.1 Primary Effectiveness Estimand**

The primary estimand is the treatment difference of Restylane Lyft with Lidocaine versus a comparator-control for augmentation of the chin region to improve the chin profile by comparing change from baseline in the Blinded Evaluator live assessment of the GCRS at 3 months after last treatment, in all randomized subjects (ITT Population). To address the impact of intercurrent events, sensitivity analyses will be performed separately from the primary endpoint analysis as outlined in [Section 9.1.3](#).

| Primary Endpoint  | Estimand  |   |
|---|---|---|
| Change from baseline in the Blinded Evaluators' live assessment using the GCRS at 3 months after last treatment | Population: all randomized subjects (ITT Population)   |   |
|   | Endpoint: The subject's GCRS based on Blinded Evaluator's live assessment at Month 3 after last treatment  |   |
|   | Intercurrent Events: 
 
1. Use of prohibited treatment in or near the treatment area prior to 3 Months after last treatment.
 
2. Use of Hyaluronidase prior to 3 Months after last treatment.
 
3. Missed visit, early termination, or missing Blinded Evaluator's live assessment of the GCRS leading to missing 3 Months after last treatment observation.
 
4. Administered treatment not according to randomization.
 
5. Subjects who were Lost to Follow Up prior to Visit 4 and re-
 
 | Handling of Intercurrent Events: 
 
1. Use observed response.
 
2. Use observed response.
 
3. Use multiple imputation (MI).
 
4. Use observed response.
 
5. Assume "No Change from Baseline".
 
 |

Confidential

Statistical Analysis Plan Version #1.0

Page 31 of 63

Effective date: 2024-05-29 18:37

Effective

Version: 1.0

Galderma

Protocol number: 43USCH2208

Protocol V4.0

|  |   |  |
|--|---|--|
|  | enrolled after discontinuation.   |  |
|  | Summary measure: Treatment Difference of Restylane Lyft with Lidocaine versus Juvéderm Voluma XC (control) using the GCRS in average change from Baseline. |  |

Note: Intercurrent events are defined as events occurring after treatment initiation that affect either the interpretation or the existence of the measurement associated with the clinical question.

### 9.1.2 Primary Effectiveness Analysis

The primary effectiveness analysis is a test to demonstrate non-inferiority of Restylane Lyft with Lidocaine to a comparator-control Juvéderm Voluma XC in the ITT and PP Population analysis sets, using the confidence interval (CI) approach.

The change from baseline in GCRS, as assessed by the Blinded Evaluator, will be analyzed using a mixed effect model with treatment and Baseline GCRS value as fixed effects. The change from baseline at Month 3 after last treatment, will be the response variable, as specified below:

$$Y(\Delta) = \beta_0 + \beta_1 \text{Treatment Group} + \beta_2 \text{Baseline GCRS value} + \varepsilon_i$$

Where:

- $Y(\Delta)$  is the change from Baseline to Month 3 after last treatment in GCRS value;
- $\beta_k$  is the slope of a given covariate (i.e., fixed effect),  $k=1,2$ ;
- $\varepsilon_i$  is the error for subject  $i$ ,  $\varepsilon_i \sim MVN(0, \sigma^2)$ ;
- $\beta_0$  is the fixed intercept.

The maximum likelihood (ML) will be used for the model estimation method.

Missing Month 3 after last treatment BE GCRS values will be imputed using Multiple Imputation (MI). The MI methods are detailed in [Section 11.6](#).

The two-sided 95% CI around the Least Square (LS) mean estimate of the Restylane Lyft with Lidocaine – Control difference will be obtained from the model and used for assessing non-inferiority in the following way: non-inferiority will be established if the upper limit of the CI for the mean difference between treatment groups is below the non-inferiority margin of 0.5 units. Superiority will be declared if the upper limit of the CI for the mean difference between treatment groups is below 0. Non-inferiority must be shown for both ITT and PP Populations. If non-inferiority is shown in the ITT and PP Population, superiority will be declared if the upper limit is below 0 in the ITT Population. This decision criterion is consistent with a gate-keeping strategy (testing for superiority following the test for non-inferiority) to maintain the overall type I error rate at 2.5%.

Galderma

Protocol number: 43USCH2208

Protocol V4.0

The null and alternative hypotheses are stated below.

$\Delta$ = the LS mean estimate of (Restylane Lyft with Lidocaine - Juvéderm Voluma XC), the statistical hypotheses to be tested are:

$H_0: \Delta \geq 0.5$

$H_1: \Delta < 0.5$

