### 3.2.1 Randomization Methodology

Approximately 174 subjects will be randomized (2:1) to treatment with either Restylane Lyft with Lidocaine (Treatment Group) or Juvéderm® Voluma™ XC (Control Group).

Before starting the study, a computer-generated randomization list will be prepared under the supervision of a designated biostatistician from the Sponsor. The randomization will be stratified by FST (I-III, IV or V-VI). Subjects in the FST I-III stratum will be further stratified by study site; subjects in the FST IV, or FST V-VI strata will not be further stratified by study site due to the smaller sample size in these groups.

Randomization will be performed using an Interactive Response System by assigning each subject to treatment with Restylane Lyft with Lidocaine or Juvéderm Voluma XC

Galderma

Protocol number: 43USCH2208

Protocol V4.0

according to the randomization list. Randomization numbers will be allocated in ascending sequential order to each subject.

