### 3.2.3 Sample Size Justification

Approximately 174 subjects will be treated in the study, randomized in a 2:1 ratio (116 with Restylane Lyft with Lidocaine: 58 with Juvéderm Voluma XC).

For sample size calculation of 174, it was assumed that the true effectiveness of Restylane Lyft with Lidocaine compared to control treatment assessed by the GCRS is approximately 0.1 point lower. A common standard deviation of 0.7 point was assumed for the treatments. Based on the non-inferiority margin of 0.5, a total sample size of 147 evaluable subjects is then required to show non-inferiority of Restylane Lyft with Lidocaine to the control treatment with a power of 90%, using a two-sided 95% CI for the difference between treatment means.

The GCRS scale is designed so that a complete scale step considers a meaningful clinical difference. A change of up to 0.5 points is not considered clinically important, thus, the non-inferiority margin of 0.5 is chosen. We have estimated the standard deviation from previous studies where the scale GCRS has been used.

Accounting for approximately 15% dropouts and non-evaluable subjects due to protocol deviations at 3 months, a total of approximately 174 subjects will be randomized in the study.

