## 11.3 Pooling of Sites

As this is a multi-center study, it is possible that some sites may only enroll a small number of subjects. Since this study plans to conduct site-level analyses, the number of subjects at each site may need to be considered for reliable and accurate results. If any site enrolls 5 or fewer subjects, the site will be removed from analyses. Sites enrolling 5 or fewer subjects will still be presented in descriptive statistics analyses.

If no sites enroll 5 or fewer subjects, then the efficacy site-level analyses will be presented for all sites.

Galderma

Protocol number: 43USCH2208

Protocol V4.0

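### The primary model omits the randomisation strata (FST cohort, site) and is fitted by ML: the interval is conservative and wider than needed if the strata matter, and about 1% too narrow from ML

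*SAP*

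**What the plan says.** - **Randomisation (SAP 3.2.1, Protocol 5.5).** "The randomization will be stratified by FST (I-III, IV or V-VI"). Subjects in FST I-III are further stratified by site; those in FST IV and V-VI are not. With up to 12 centres (Protocol 3.3) that is up to 12 + 2 = 14 strata.
- **Primary model (SAP 9.1.2).** The change from baseline "will be analyzed using a mixed effect model with treatment and Baseline GCRS value as fixed effects". The equation has an intercept, two slopes and one residual term, with no random effect. "The maximum likelihood (ML) will be used for the model estimation method". The protocol model (9.4.1) has no strata either.
- **Decision rule (SAP 9.1.2).** The upper 95% limit must lie below 0.5 in both ITT and PP. Superiority is then declared if the ITT limit is below 0.
- **Where the strata do appear.** Site and FST are covariates in the imputation model (SAP 11.6) and subgroup factors (SAP 11.5.1). No analysis in SAP 9.1.3 adjusts the overall treatment effect for them.
- **Small sites (SAP 11.3).** "If any site enrolls 5 or fewer subjects, the site will be removed from analyses". Descriptive statistics are exempt.

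**The concern.** Stratified randomisation balances the arms on the stratifiers. If these predict the outcome, the treatment estimate varies less than an unadjusted model assumes. The unadjusted standard error is then too large, and precision already paid for in the design is not used.

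Site is a plausible predictor because the GCRS is a live rating by a Blinded Evaluator. The plan itself tries to limit inter-observer variability (Protocol 6) and caps enrolment at 35 per site to limit bias (Protocol 3.3).

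ML raises a separate question. It divides the residual sum of squares by n instead of n minus the number of fitted parameters, which narrows the interval. A single confidence limit decides both non-inferiority and superiority, so it matters whether either effect is large enough to count.

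**Working it through.** **1. The plan's own figure (SAP 3.2.3).** Inputs: "Based on the non-inferiority margin of 0.5, a total sample size of 147 evaluable subjects is then required"; true effectiveness "compared to control treatment assessed by the GCRS is approximately 0.1 point lower"; "A common standard deviation of 0.7 point was assumed for the treatments"; "with a power of 90%, using a two-sided 95% CI for the difference between treatment means"; allocation 2:1.

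Control n = (1 + 1/2) × 0.7² × (1.960 + 1.282)² / (0.5 − 0.1)² = 48.3, so 49 control + 98 test = **147**. This matches. Power at 49/98 is 90.4% (normal) or 90.0% (noncentral t). Then 147/0.85 = 172.9, so 173, or 174 for 2:1. The strata do not enter this calculation.

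**2. Effect of ML (three fixed-effect parameters, no random effect).** SE ratio = √((n − 3)/n).

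| n | SE ratio | Half-width, n − 3 divisor | Half-width, ML | One-sided error, ML |
|---|---|---|---|---|
| 147 | √(144/147) = 0.990 | 0.242 | 0.240 | 2.62% |
| 174 | √(171/174) = 0.991 | 0.222 | 0.220 | 2.60% |

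These use t limits on n − 3 degrees of freedom. With normal limits the errors would be 2.72% and 2.68%. Either way the upper limit moves by about 0.002 against a margin of 0.5.

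**3. Effect of omitting the strata.** Let R² be the share of residual variance explained by FST and site. Ignoring degrees of freedom, adjustment multiplies the SE by √(1 − R²): 0.975, 0.949 and 0.894 at R² of 5, 10 and 20%. The documents give no R² and no block size, so both are assumptions.

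Simulation: 10,000 trials per scenario, 12 sites, 14 strata, permuted blocks of 6, SD 0.7, normal outcome, no missing data. The adjusted model has fixed site and FST terms and uses the residual degrees of freedom. Power is at a true difference of 0.1.

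| R² | Error, SAP model, n=147 | Error, SAP model, n=174 | Power, SAP model, n=147 | Power, adjusted, n=147 | Half-width, SAP → adjusted, n=147 |
|---|---|---|---|---|---|
| 0 | 2.91% | 2.35% | 89.3% | 88.3% | 0.240 → 0.246 |
| 5% | 2.49% | 2.14% | 90.3% | 90.3% | 0.240 → 0.240 |
| 10% | 2.09% | 2.12% | 90.9% | 91.8% | 0.240 → 0.233 |
| 20% | 1.66% | 1.81% | 91.9% | 94.9% | 0.240 → 0.220 |

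The Monte Carlo SE of the error is √(0.025 × 0.975/10,000) = 0.16 points. The two values at R² = 0 lie either side of the analytic 2.6%, which is the figure to use there. At n=174, where power is already about 94 to 96%, the gains are smaller: 94.8 to 95.7% at R² = 10% and 95.8 to 97.4% at 20%.

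At R² = 0 and n=147, power is 89.3% (ML), 88.8% (same model, n − 3 divisor) and 88.3% (adjusted). About half of the one-point loss therefore comes from removing the ML shortcut.

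**4. Second simulation.** 3,000 trials per scenario, blocks of 3, 174 randomised, 15% lost. With site explaining 10 or 20% of variance, the unadjusted SE is too large by 0.1212/0.1173 = 1.03 and 0.1210/0.1134 = 1.07. One-sided error is 2.1% and 1.6%. Adjustment raises power from 91.3 to 92.4% and from 91.5 to 94.1%. With no strata effect, power falls from 89.8 to 89.2%.

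**The case against.** - **The two effects oppose each other.** A reader might infer that the interval inflates false claims of non-inferiority. It does not when the strata matter: omitting them is conservative for both non-inferiority and superiority. Only the ML effect is anti-conservative, and it is about 1% of the SE. This stands.
- **The planned power is met anyway.** Simulated power of the SAP model is 89 to 92% at 147 evaluable. This stands: the trial is not underpowered because of this choice.
- **The gain is conditional.** The endpoint is a change score and the same evaluator should rate a subject throughout where possible (Protocol 5.6), so a rater's constant severity at least partly cancels. A small R² is possible, and below about 5% adjustment does not pay. Block size is also assumed; blocks of 3, the smallest for 2:1, favour showing a conservative unadjusted analysis. These points stand as limits on the size.
- **The imputation model is richer than the analysis model.** A reader might call this a mismatch. Extra covariates in the imputation model are accepted practice, and treatment and baseline GCRS are in it.
- **SAP 11.3 might seem to remove randomised subjects from ITT.** Its neighbouring sentences speak of site-level analyses, and SAP 5.1 keeps all randomised subjects. The wording is loose, not contradictory in context.
- **ML with 16 parameters would shrink the SE by about 5%** (√(158/174) = 0.953). That is a larger model than the SAP's. It is only a reason to bring in the strata and REML together.
- **Part of SAP 9.1.2 may be unseen.** Text after the hypotheses is missing from the public copy, and Kenward-Roger is in the abbreviation list but not in the visible model text. A degrees-of-freedom method may therefore be stated already. It would not by itself put the strata into the model.

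**Conclusion.** The point holds in a limited form. The deciding model does not reflect the stratified randomisation, and no listed sensitivity analysis fills that gap. If FST and site explain 10 to 20% of the variance, the interval is conservative (one-sided error about 2.1 to 1.7%) and adjustment is worth about 1 to 3 points of power at 147 evaluable. Near 5% it is neutral; at zero it costs about 0.6 to 1 point. ML on its own gives a one-sided error of about 2.6% and matters only if the upper limit falls within about 0.002 of 0.5 or 0.

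The documents do not support reading this as an invalid test, an underpowered trial or a breach of ITT. The figures assume normal outcomes, 12 sites and the stated block sizes, leave out between-imputation variance, and use fixed site effects in the main simulation's adjusted model. The random intercept proposed below was not simulated.

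**What to change.** In SAP 9.1.2, pre-specify one model for the ITT, PP and sensitivity runs that repeat the primary analysis: change = treatment + baseline GCRS + FST cohort at randomisation (three levels) as fixed effects, with site as a random intercept. Fit it by REML with t-based limits and name the degrees-of-freedom method if it is not already stated. Site applies to all FST cohorts because every subject is rated at a site, although randomisation uses site only within FST I-III. Record the change in SAP 15.2, before any treatment-level results are seen.

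In SAP 11.3, say that the rule for sites with 5 or fewer subjects applies to site-level analyses only, and that no randomised subject is dropped from the ITT or PP primary analysis because of site size.

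Cost: SAP wording and one model statement, with no new data. If the strata explain nothing, power falls by about 0.6 to 1 point.

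### The deciding confidence limit comes from a common-variance model under 2:1 allocation; letting the residual variance differ by arm would protect the 2.5% error rate at almost no cost

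*SAP*

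**What the plan says.** SAP 9.1.2 states that the Month 3 change in Blinded Evaluator GCRS "will be analyzed using a mixed effect model with treatment and Baseline GCRS value as fixed effects". That sentence gives only the mean structure. The variance assumption is in the definition of the error term below the equation: a single sigma-squared, with no index for arm. On estimation the section says "The maximum likelihood (ML) will be used for the model estimation method".

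The two-sided 95% limit from this fit decides the trial. Its upper end must lie below 0.5 in both ITT and PP, and superiority is then read from the same limit against 0 in ITT. The section says this holds the type I error at 2.5%.

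The arms are unequal in size: SAP 3.2.1 says "Approximately 174 subjects will be randomized (2:1) to treatment with either Restylane Lyft with Lidocaine" or the comparator, and SAP 3.2.3 gives the numbers as "randomized in a 2:1 ratio (116 with Restylane Lyft with Lidocaine: 58 with Juvéderm Voluma XC". On spread, SAP 3.2.3 says "A common standard deviation of 0.7 point was assumed for the treatments" and "We have estimated the standard deviation from previous studies where the scale GCRS has been used". No SD is given for either product.

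The sensitivity analyses in SAP 9.1.3 that keep the mean difference change the handling of missing data, the exclusions or the population, and refit the same model. The ordinal regression there gives odds ratios and an expected change per arm, with no confidence limit to compare with 0.5.

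**The concern.** With equal arms, a pooled variance gives the right standard error for a difference in means even if the arms differ in spread. With 2:1 allocation it does not. The pooled variance takes about two thirds of its weight from Restylane, the larger arm, whereas the true variance of the difference takes most of its weight from Voluma, the smaller one. If the SDs are equal this does not matter. If they differ, the limit is misplaced.

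The consequence depends on which arm is more variable. If it is Voluma, the upper limit is too low and false non-inferiority exceeds 2.5%. If it is Restylane, the limit is too high, the test is conservative and power is lost. Requiring success in ITT and PP does not correct this, because both use the same variance assumption on largely the same subjects.

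**Working it through.** **The plan's own figure.** Inputs from SAP 3.2.3: SD 0.7, margin 0.5, true effect of Restylane that "is approximately 0.1 point lower" than control, 90% power, two-sided 95% CI, ratio 2:1. Voluma n = 0.7² × (1 + 1/2) × (1.960 + 1.282)² / (0.5 − 0.1)² = 48.3, so 49. Restylane n = 98. The total is 147, matching "Based on the non-inferiority margin of 0.5, a total sample size of 147 evaluable subjects is then required". Then 147/0.85 = 172.9, rounded up to 173, and the next multiple of 3 is 174. The sample size reproduces.

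**Formulas at 98:49.** With residual SDs sR (Restylane) and sV (Voluma):

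- True SE² = sR²/98 + sV²/49.
- Model SE² = [(97 sR² + 48 sV²)/145] × (1/98 + 1/49).
- Because 1/98 + 1/49 = 3/98 and the pooled weights are about 2/3 and 1/3, the model SE² is about sR²/49 + sV²/98. In effect each arm's variance is divided by the other arm's sample size.
- One-sided error at a true difference of 0.5 = Φ(−1.976 × model SE / true SE), where 1.976 is the t quantile on 145 df.
- Power at a true difference of 0.1 = Φ((0.4 − 1.976 × model SE)/true SE) with one variance, and Φ(0.4/true SE − Welch t) with separate variances.

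**Results.** The unequal SDs are assumptions; the documents give only 0.7 for both arms.

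| SD Restylane/Voluma | True SE | Model SE | Ratio | One-sided error | Power, one variance | Power, separate |
|---|---|---|---|---|---|---|
| 0.8/0.6 | 0.1178 | 0.1294 | 1.10 | 1.5% | 89% | 92% |
| 0.7/0.7 | 0.1225 | 0.1225 | 1.00 | nominal | 90.1% | 90.0% |
| 0.6/0.8 | 0.1294 | 0.1177 | 0.91 | 3.6% | 90% | 86% |

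In both unequal rows the limit is displaced by 1.976 × 0.0116 to 0.0117 = 0.023 grade. With equal SDs the loss from separate variances is between 0.1 and 0.2 points.

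**Wider range.** Holding the pooled SD at 0.7, using 1.96, and varying the ratio sV/sR, the error is 0.8% at 0.5, 1.7% at 0.8, 2.5% at 1.0, 3.4% at 1.25, 4.3% at 1.5 and 5.5% at 2.0. At 116:58 the values are almost the same. Simulated ANCOVA with Baseline GCRS as covariate (100,000 runs per case) agrees: 3.5% at 1.25 and 4.2% at 1.5. With separate variances and small-sample df the simulated error stays between 2.5% and 2.65% across the whole range.

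**Isolating the cause.** At 87:87 the analytic error is 2.5% at every ratio, so the effect comes from 2:1 allocation combined with one variance. ML estimation adds only about 0.1 point at equal SDs and is a separate matter.

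**Which direction is likelier.** At the null boundary Voluma is better by 0.5, so its scores lie nearer the floor of 0, where there is less room to vary. I took a rounded normal latent score with assumed inputs: the same latent SD in both arms (0.5 to 0.9), baseline grades 1 and 2 with 30% to 70% at grade 1, and a Voluma mean change of −0.8 to −1.2. In all 45 combinations Voluma had the smaller residual SD (ratio 0.46 to 0.94), and the error was about 0.7% to 2.2%. Other shapes can reverse this: four invented grade distributions with a true difference of 0.5 to 0.57 gave ratios from 0.62 to 1.49 and errors from 1.1% to 4.2%.

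**The case against.** The strongest reply is that nothing in the documents shows a difference in spread. Both products are cross-linked hyaluronic acid gels at 20 mg/mL with 0.3% lidocaine, injected under the same rules toward the same correction target, and constant-variance ANCOVA is conventional. The displacement is about 0.02 grade against a margin of 0.5, so it changes the decision only when the limit falls very close to 0.5. SDs and change-from-baseline categories will be tabulated by arm, so unequal spread would be visible. The ordinal analysis assumes no common residual variance. All of this stands, and it limits the point to an improvement. It does not remove the point: the 2.5% claim still rests on an assumption that is neither supported per product nor tested by a limit set against 0.5.

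A reader might infer that a bounded scale makes inflation above 2.5% the expected outcome. The documents do not support that. Boundedness is a reason not to presume equal spread, but in the simple model above it points the other way.

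Part of SAP 9.1.2 may also not be visible. SAP 11.6 refers to it for re-enrolled subjects whom the readable text does not mention, and a Kenward-Roger abbreviation is defined but not used in the readable text. Further model detail cannot be excluded. The stated error term is nevertheless explicit, and a df correction alone would not separate the variances.

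**Conclusion.** The point holds as a conditional statement. Under 2:1 allocation, the error rate stated in SAP 9.1.2 is exact only if the two arms share one residual SD, and the plan gives no product-specific support for that. For assumed SDs of 0.8/0.6 and 0.6/0.8 the one-sided error is about 1.5% and 3.6%. The direction is unknown. The likelier cost is lost power, about 3 points at 0.8/0.6, while inflation remains possible under other distributions.

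Three stronger readings are not supported: that the trial's error rate does exceed 2.5%, that the products are known to differ in variability, and that the sample size is wrong. The figures of 147 and 174 reproduce and are not challenged.

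**What to change.** In SAP 9.1.2 keep the same mean model and let the residual variance differ by arm: in PROC MIXED, REPEATED / GROUP=treatment with Satterthwaite or Kenward-Roger df. A heteroscedasticity-robust standard error is an alternative. Apply it in each imputed dataset before combining, and in PP, and take the deciding 95% limit from that fit. If the common-variance model is kept as primary, add this fit to SAP 9.1.3 as a pre-specified sensitivity analysis judged against 0.5.

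The cost is one line of SAS and one sentence in the SAP. If the SDs are equal, about 0.2 points of power are lost. If Voluma is the more variable arm, power is lower than the common-variance limit would show (about 86% against 90% at 0.6/0.8), because that limit gains its extra power by exceeding 2.5%. If Restylane is the more variable arm, power rises, to about 92% from 89% at 0.8/0.6.
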